1.4. Sample Size Determination

1.4.1. Originally Planned Sample Size

To evaluate the effect of apalutamide on ventricular repolarization in a subset of patients, the sub-study was planned to enroll at least 100 patients to ensure that at least 60 patients treated with apalutamide will provide at least 98.7% power to detect a true effect of 10 msec change from baseline considering only the active group. Details for the power calculation and statistical assumptions are provided in protocol.

1.4.2. Achieved Sample Size and Change in Planned Analysis

As a consequence of slow patient's enrollment to the QT substudy, approximately 17 subjects were randomized by the clinical cutoff date, which is only 17% of the originally planned sample size. To be consistent with this change, no hypothesis testing will be performed and all planned statistical analysis in the QT substudy will be performed for an estimation purpose.

1.5. Randomization and Blinding

The subset of 100 patients at selected sites will undergo the same screening procedures as the main protocol in order to be randomized into the study, following the same Inclusion/Exclusion criteria. Both apalutamide and placebo patients will be enrolled in a blinded manner as per the main protocol randomization criteria.

2. GENERAL ANALYSIS DEFINITIONS

2.1. Handling of Missing Data and Imputation of Missing Dates

Missing test results or assessments will not be imputed.

ARN-509 Statistical Analysis Plan ARN-509-003 QT Study For missing dates, in general, imputation of missing dates will be made for AE onset date, AE resolution date, start and end dates of prior and concomitant medications.

- If dates are completely missing, no imputation will be made. For any partial date with missing year, no imputation will be made.
- If only day is missing, then the 15th of the month will be used.
- If only year is present, then June 30th will be used.
- If such imputed date for prior or concomitant medication start date is in the same year and month but on or after date of first dose, then date of first dose 1 will be used. If the imputed medication start date is after the medication end date, then the medication end date will be used. If the imputed date is for a medication start date and is in the same year and month but after the date of post-study follow-up contact (10±2 days after the last dose of study drug), then the date of post-study follow-up contact will be used.
- If the imputed date for a medication end date is in the same year and month but is before the first dose date, then the first dose date will be used. If the imputed date for a medication end date is after the date of post-study follow-up contact (10±2 days after the last dose of study drug), then the follow-up contact date will be used, or if the imputed medication end date is before the medication start date, then the medication start date will be used.
- If the imputed date for an AE start date is in the same year and month but is before the first dose date, then the first dose date will be used. If the imputed AE start date is after the AE end date, then the AE end date will be used. If the imputed date is for an AE start date and is in the same year and month but after the date of post-study follow-up contact (10±2 days after the last dose of study drug), then the date of post-study follow-up contact will be used.
- If the imputed date for an AE end date is in the same year and month but is before the first dose date, then the first dose date will be used. If the imputed date for an AE end date is after the date of post-study follow-up contact (10±2 days after the last dose of study drug), then the follow-up contact date will be used, or if the imputed AE end date is before the AE start date, then the AE start date will be used.

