#### **8.8 SAFETY FOLLOW-UP (28 DAYS FOLLOWING THE LAST DOSE OF STUDY DRUG)**

- Record any adverse events
- Record changes to concomitant medications

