### 13.3.1 Analysis of Adverse Events

Adverse events (AEs) will be graded according to the NCI Common Terminology Criteria for Adverse Events (CTCAE) Version 4.0 and coded to preferred term and system organ class (SOC) using the most recent version of MedDRA.

All AEs reported from the first dose of study drug until 28 days after the last dose of study drug will be considered as treatment-emergent AEs and will be summarized by treatment arm.

For each treatment arm, adverse event incidence rates will be summarized with frequency and percentage by MedDRA SOC and preferred term, with all patients treated in that treatment arm as the denominator, unless otherwise specified. In addition, AE incidence rates will also be summarized by severity and relationship to study drug. Treatment-related AEs are those judged by the Investigator to be at least possibly related to the blinded study drug. Adverse events with missing severity or relationship to study drug will be classified as severe and treatment-related, respectively. Patients with multiple occurrences of events will only be counted once at the maximum severity to study drug for each preferred term, SOC, and overall. Deaths that occur within 28 days after the last dose of study drug are defined as on-study deaths.

Summary tables and individual patient listings will be prepared as per the Statistical Analysis Plan. An additional analysis by formulation subgroups will be performed as outlined in the Statistical Analysis Plan.

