7.6 SAFETY ANALYSES

7.6.1 Adverse Events

Patients will be assessed for adverse events at each monthly clinic visit while on the study. Adverse events (AEs) will be graded according to the NCI Common Terminology Criteria for Adverse Events (CTCAE) Version 4.0 and coded to preferred term and system organ class (SOC) using the most recent version of MedDRA.

All AEs reported during the AE reporting period (inclusive of the 28-day post last dose of study drug period) will be considered as treatment-emergent adverse events and will be summarized by treatment group as treated using all patients in the SAFETY population.

For each treatment group, adverse event incidence rates will be summarized with frequency and percentage by MedDRA SOC and preferred term, with all patients treated in that treatment group as the denominator, unless otherwise specified. In addition, AE incidence rates will also be summarized by severity and relationship to study drug. Treatment-related AEs are those judged by the Investigator to be at least possibly related to the blinded study drug. Patients with multiple occurrences of events will only be counted once at the maximum severity to study drug for each preferred team, SOC, and overall. Deaths that occur within 28 days after the last dose of study drug are defined as on-study deaths.

Summary tables of the following AEs will be provided:

ARN-509-003	
Statistical Analysis Plan v7.0 26 June 20	17

Page 17 of 34

- Overall summary of AEs: the number and percentage of patients who experienced any AE, any serious adverse event (SAE), any treatment-related AE, any treatment-related SAE, any discontinuations due to an AE, and any deaths
- All AEs by SOC and preferred term
- All AEs by SOC, preferred term, and toxicity grade
- All AEs by decreasing frequency of preferred term
- Grades 3 or 4 AEs by SOC, preferred term and toxicity grade
- Drug-related AEs by SOC and preferred term
- Drug-related AEs by SOC, preferred term, and toxicity grade
- Drug-related Grades 3 or 4 AEs by SOC, preferred term and toxicity grade
- AEs that led to study drug discontinuation by SOC and preferred term. Study drug discontinuation will be determined from the End of Treatment CRF (where reason for termination is "Adverse Event") and the specific AE will be determined from the AE CRF page (where action taken is "Withdrawn from Study")
- AEs that led to study drug discontinuation by SOC, preferred term, and toxicity grade.

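### The QT sub-study SAP's partial-date rules rely on a 10±2-day contact this trial does not have and can place some adverse events outside the treatment-emergent window

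*SAP*

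**What the plan says.** Section 2.1 of the QT sub-study SAP fills in partial AE and medication dates in two steps.

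- **Fill-in.** "If only day is missing, then the 15th of the month will be used". "If only year is present, then June 30th will be used".
- **Adjustment for AE onset.** The date moves up to first dose under this condition: "If the imputed date for an AE start date is in the same year and month but is before the first dose date". It moves back to the follow-up contact only if it falls in the contact's year and month. The contact is defined as "the date of post-study follow-up contact (10±2 days after the last dose of study drug".
- **Adjustment for end dates.** The AE rule opens "If the imputed date for an AE end date is after the date of post-study follow-up contact", and the contact date then replaces the imputed one. The medication end-date rule is parallel. Neither has a same-month condition.

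The rest of the trial works to 28 days. Protocol section 8.8 is headed "SAFETY FOLLOW-UP (28 DAYS FOLLOWING THE LAST DOSE OF STUDY DRUG". Protocol section 13.3.1 treats as treatment-emergent "All AEs reported from the first dose of study drug until 28 days after the last dose of study drug", and the note under the table shell in main SAP Appendix 2 gives the same window. Main SAP section 7.6.1 is worded differently: "All AEs reported during the AE reporting period (inclusive of the 28-day post last dose of study drug period". QT SAP section 3 takes over the main-study safety analyses, restricted to sub-study patients. The main SAP has no partial-date rule of its own.

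**The concern.** The rules use the date of a contact that the study does not schedule. It is absent from protocol sections 8.7 to 8.9, the Schedule of Activities, the sub-study schedule in protocol Appendix 8 and the main SAP. A programmer would have to invent that date.

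There is a separate gap in the first-dose protection. A year-only onset always lands in June, so the same-month condition cannot rescue it when first dose is in another month.

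At stake is whether a partially dated AE in the sub-study counts as treatment-emergent, and whether imputed end dates stay consistent with what the site recorded.

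**Working it through.** The plan gives no figure to reproduce. The check applies the section 2.1 rules to every date of a non-leap year.

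**Inputs**
- Fill-in values: the 15th, or June 30 (QT SAP 2.1).
- Contact: last dose + 8, + 10 or + 12 days (QT SAP 2.1).
- Window: first dose to last dose + 28 days (protocol 13.3.1; main SAP Appendix 2 note).
- The same-year-and-month condition is read as the month of the reference date (first dose or contact).

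**1. Year-only onset in the year of first dose.** June 30 precedes every first dose from 1 July to 31 December: 31 + 31 + 30 + 31 + 30 + 31 = 184 dates, and 184/365 = 50.4%. The imputed onset is 1 to 184 days before first dose, and the months never match, so nothing corrects it. An AE that began on treatment is dated before treatment.

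**2. Year-only onset in the year of last dose.** The same gap exists at the other end. With the contact at day 10, last doses from 1 January to 21 May (31 + 28 + 31 + 30 + 21 = 141 dates) put June 30 after last dose + 28 days, while the contact falls before June, so no limit applies. With the contact at day 8 or day 12 the count is 143 or 139, that is 38% to 39% of dates.

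**3. Day-missing onset on days 15 to 28 after last dose.** There are 14 × 365 = 5110 combinations of last-dose date and true onset day. Suppose last dose + 28 days is the d-th of a month, with d from 1 to 14. An onset on the 1st to the d-th of that month is inside the window but is imputed to the 15th, which is outside.
- Number of such combinations: 12 × (1 + 2 + … + 14) = 12 × 105 = 1260, and 1260/5110 = 25%.
- The contact falls 28 − 12 = 16 to 28 − 8 = 20 days before the window closes, hence in the previous month. The same-month condition fails and no limit applies.
- With the anchor at last dose + 28 days, the months match and the onset is set to the last day of the window. The count falls from 1260 to 0.

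**4. Does the day-10 limit itself remove AEs from the window?** No.
- Day-missing onsets: the limit acts when the contact falls on the 1st to 14th, 12 × 14 = 168 last-dose dates. The 15th is then at most day 22 to 26 after last dose, already inside the window. Status changes in 0 of 168.
- Year-only onsets: the limit acts for 29 last-dose dates and changes status for 9 to 13 of them, always moving the AE into the window.

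**5. End dates.** Take a last dose on 1 March and a resolution recorded as June with the day missing. The imputed 15 June is after the contact (1 March + 10 = 11 March) and is replaced by 11 March. The recorded month is overridden, although protocol section 9.2.2 has AEs followed until resolved or stable.

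**6. Cost of a day-28 anchor.** For true onsets from day 29 to day 60 (32 × 365 = 11680 combinations), the number of day-missing onsets imputed inside the window rises from 1523 to 5373. Protocol section 9.2.2 records non-serious AEs only to day 28, so few such late events should be in the data.

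**The case against.** **The limit lies inside the window, so it cannot push an AE out.** This stands (step 4). A reader might infer that truncation at day 10 causes the misclassification. It does not: the year-only gaps and the mismatch between the day-10 anchor and the 28-day window do.

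**Shortened end dates reach no planned summary.** This largely stands. Treatment-emergent status does not depend on the AE end date, the AE tables in main SAP section 7.6.1 are incidence tables, and a medication cut back to day 8 to 12 still counts as concomitant. What remains is wrong imputed end dates and durations.

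**A pre-dose imputed onset may still be counted.** This stands in part. Main SAP section 7.6.1 refers to the AE reporting period, and protocol section 9.2.2 starts recording at consent, so on that wording the AE need not drop out. Protocol section 13.3.1 and the main SAP Appendix 2 note start at first dose, and on those it does. The documents leave this open.

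**Year-only dates should be uncommon.** This is plausible but not quantified. AEs are recorded at every clinic visit, each 4-week cycle at first, and the data are queried. A reader might take 50.4% to mean that about half of patients have a misclassified AE. It is the share of first-dose dates at which a year-only onset in that year would be misplaced.

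**Main-study tables are untouched.** A reader might infer that the rule carries over to the main tables, or that main and sub-study counts will differ. The rule sits in the QT plan only, and the main SAP does not state how it handles partial dates, so neither can be shown.

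**Conclusion.** The point holds as a small correction. Section 2.1 uses a contact that this trial does not schedule, and its rules can date some partially recorded AEs outside a window that the trial sets at first dose to last dose + 28 days. Two routes matter most: year-only onsets before a July to December first dose (184 of 365 dates), and day-missing onsets late in the 28-day window (1260 of 5110 combinations).

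These counts weight all calendar dates equally and apply only to records with a partial date, whose frequency the documents do not give. They support saying that AEs can be misclassified, not that they are. The first route also depends on the protocol 13.3.1 and Appendix 2 definition rather than the main SAP 7.6.1 wording.

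The consequence is limited. QT SAP section 1.4.2 reports about 17 patients randomized and no hypothesis testing, and the QTc analyses do not use AE or medication dates.

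**What to change.** In QT SAP section 2.1:

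1. Replace the 10±2-day contact with last dose + 28 days in the onset rules.
2. When the month is missing, compare on year alone at both ends. If the recorded year is that of first dose and June 30 falls before first dose, set the onset to first dose unless a recorded AE end date precedes it. If the recorded year is compatible with onset by last dose + 28 days and June 30 falls later, set the onset to last dose + 28 days.
3. Do not let an end-date limit override a recorded month or year.

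Also reconcile the treatment-emergent wording in protocol section 13.3.1, main SAP section 7.6.1 and the main SAP Appendix 2 note.

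The cost is a few lines of SAP text and a small programming change. The downside is that a few true screening-period AEs with partial dates would count as treatment-emergent, as could the occasional late onset in step 6 of the working. Both err in the conservative direction for safety.

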2.2. Correction Methods for QTc Calculations

The ECG parameters, heart rate (HR), PR, RR, QT, QRS, PR intervals will be measured in triplicates from the 12-lead ECG at the time points specified in protocol. The measured QT data will be corrected for heart rate using Fridericia (QTcF) Bazett (QTcB) and study-specific power (QTcP)correction methods, as per the following formulae/method (with QT, RR and QTc's expressed in msec):

1. Fridericia's Correction

$$QTcF = \frac{QT}{\left(RR/1000\right)^{(1/3)}}$$

ARN-509 Statistical Analysis Plan ARN-509-003 QT Study 2. Bazett's Correction

$$QTcB = \frac{QT}{\left(RR/1000\right)^{0.5}}$$

3. Study-specific Power Correction

A linear regression model will be fitted with logarithm of baseline (predose) QT interval as the dependent variable and logarithm of corresponding RR interval as the predictor variable. The slope of the regression line will be estimated from this model. Using the estimated slope (b) of the regression line, the study-specific power corrected QTcP will be calculated using the formula:

$$QTcP = \frac{QT}{(RR/1000)^b}$$

In this study, the primary correction method was the Fridericia's corrected QT interval (QTcF).

2.3. Schedule of ECG and PK Data Collections

Digital 12-lead ECG equipment will be provided to each clinical site participating in this substudy by the central laboratory for the duration of the sub-study.

ECGs should be collected after the patient has rested quietly and is awake in a fully supine (or semi-recumbent, if supine is not tolerated) position for 10 minutes, and prior to any blood collection. For each patient the same position (eg, supine or semi-recumbent) should be used for all ECGs collected. Starting on Cycle 1 Day 1, time point matched blood samples for PK analyses will be collected immediately following the collection of ECGs and before the collection of blood for all other clinical evaluations. ECGs will be read by independent cardiologists from the central laboratory in a blinded manner and via single reader paradigm. QT/QTc intervals of each subject will be assessed by using a pre-specified lead (primary Lead V3 or backup Lead II).

The schedule of activities specific to this ventricular repolarization sub-study is as follows. All other assessments at the other time points will follow the Schedule of Activities in the main protocol.

- Cycle 1 Day 1
 - Hour -1 pre-dose:
 - Collect a set of triplicate 12-lead ECGs, 2 minutes apart;
 - Hour 0 pre-dose:
 - Collect a second set of triplicate 12-lead ECGs, 2 minutes apart;
 - Collect one blood sample for PK analysis;

ARN-509

Statistical Analysis Plan ARN-509-003 QT Study

- Hour 2 and Hour 4 post-dose:
 - Collect a set of triplicate ECGs, 2 minutes apart;
 - Collect one blood sample for PK analysis;
- Cycle 3 Day 1
 - Hour 0 pre-dose:
 - o Collect a set of triplicate 12-lead ECGs, 2 minutes apart;
 - Collect one blood sample for trough PK analysis;
 - Hour 2 and Hour 4 post-dose:
 - Collect a set of triplicate ECGs, 2 minutes apart;
 - Collect one blood sample for PK analysis;

		Cycle 1	Day 1	Cycle 3 Day 1			
Activities and Forms to be	Hour -1	Hour 0	2 Hours	4 Hours	Hour 0	2 Hours	4 Hours
Completed Specific to the	pre-	pre-	post-	post-	pre-	post-	post-
Sub-Study Only:	dose	dose	dose	dose	dose	dose	dose
Triplicate 12-lead ECG	Х	Х	Х	Х	Х	Х	Х
PK samples*		Х	Х	Х	Х	Х	Х

* PK samples are to be collected immediately after each ECG; the main study PK samples on Day 1 of Cycles 1 and 3 between 0.5 and 4 hours post dose do NOT have to be collected for the 100 patients on this sub-study. The 100 patients participating in this sub-study will follow the main study PK sampling schedule for the samples taken on Day 1 of Cycles 2, 6, 12, 18, and 24

2.4. Only Use the Baseline and Post-treatment QT/QTc Intervals Assessed by the Same Lead in the Calculation of Change from Baseline QT/QTc Intervals

Per agreement in "Special Protocol Assessment" (SPA) with FDA issued on 11/09/2012, for each subject, only his baseline and post-baseline QT/QTc intervals that were evaluated by the same lead will be acceptable for analysis and submission.

A primary lead (Lead V3) will be used to assess all triplicate baseline QT/QTc intervals, and all triplicate QT/QTc intervals at each post-baseline time-points. For any subject, if his/her QT/QTc intervals based on the primary lead will be unmeasurable or unsuitable at some time-points, a backup lead (Lead II) will be used to assess relevant QT/QTc intervals.

When a subject completed study and had baseline and post-treatment QT/QTc intervals not totally based on the primary lead, a "Lead Harmonization" process will be performed for the subject, in which his triplicate ECG measurements at baseline and at each of post-baseline time-points will be re-analyze by cardiologist using the backup lead (if possible).

In the calculation of change from baseline QT/QTc intervals for each patient, baseline and each post-treatment time-point QT/QTc intervals will be the average of triplicate intervals (2 minutes apart measured at the time-point) that were all assessed by the same lead.

2.5. Analysis Sets

PD Analysis Set

Pharmacodynamics (PD) analysis set will include all subjects from the sub-study who were randomized and received at least one dose of the study drug and had both predose and at least one postdose ECG measurement.

PD analysis set will be used for all ECG-related analysis (include Subject Information).

PK Analysis Set

The Pharmacokinetic (PK) analysis set will include all subjects from the sub-study who were randomized and received at least one dose of the study active drug and have estimable PK parameter Cmax. This analysis set combined with Pharmacodynamics (PD) analysis set will be used for PK/PD relation analysis.

Subjects who received placebo will not be part of the PK population.

3. SUBJECT INFORMATION AND SAFETY

All analysis planned in this section will be the same as the planned analysis in the main study except for the analysis set which will be limited to the subjects for this sub-study (defined as in Section 2.5). A list of tables and listings is presented at the DPS.

4. PHARMACOKINETICS (PK)

The apalutamide PK concentration data will be presented in listing and descriptive statistics (mean, SD, median, range). No PK inferential statistical analysis will be performed for this substudy.

5. PHARMACODYNAMICS (PD)

In this study, the primary variable of interest is the change from baseline in QTcF intervals (Δ QTcF).

For each subject, the baseline ECG parameters will be the average of the 2 sets of predose measurement taken on Cycle 1 Day 1 (Hour -1 and Hour 0).

5.1. QT/QTc Intervals

The average of the triplicate ECG measurements taken at each time point will be used for the analysis. QTc-related analyses will be performed on QTc correction methods QTcF, QTcB and QTcP.

5.1.1. Analysis of QT/QTc

• Mean QT and corrected QTc over time will be listed for each subject by treatment group and will be summarized using descriptive statistics (mean, SD, median, range) at each time point and for each treatment group.

ARN-509				Statistic	al An	alys	is Pl	an A	RN-509-0)03 Q1	ſ Study

- For each treatment group, the incidence count and percent of subjects with any postdose QTc values >450 to ≤480, >480 to ≤500, and >500 msec, will be summarized. They will also be summarized by time point for each treatment group. Subjects with QT/QTc values >500 msec will be listed.
- Mean QT and corrected QTc versus time profiles for both treatment groups will be plotted on the same graph.

